### **2. Patient selection**

We planned to enroll 1000 patients in each of the STEMI, NSTEMI and control groups.

Considering [name] Thoracic and Cardiovascular Surgery Training and Research Hospital has a large local network for primary with around 1000-1500 STEMI patients per year referred for primary PCI, it will take approximately one-year period to collect 1000 STEMI patients. This institution also receives STEMI and NSTEMI patients with a 2:1 ratio, which corresponds well to the reported incidences of these two entities. Therefore, we expected to enroll 1000 NSTEMI patients before STEMI group is completed. Another 1000 patients with a clinical picture compatible with an acute coronary event, but without any ECG changes during serial follow-up and negative and unchanging troponin levels within the first 24 hours will be enrolled. As these patients were so much in frequency, and this group would be completed at the beginning of the study, if we started at the same time with

STEMI/NSTEMI enrollment (May 1, 2017); we decided to select these patients from a computer-generated random list. Therefore, the patients in these group was enrolled after first two groups were completed (December 31, 2018). The total admission counts will also be calculated for the weighted analysis of diagnostic accuracy indexes; such as sensitivity, specificity, negative and positive predictive value. After this enrollment period we will have three cohorts.

- STEMI group: These patients should have all of the following criteria: (1) New ST-segment elevation at the J-point in two contiguous leads with the cut-point:  $\geq 1$  mm in all leads other than leads V2–V3 where the following cut-points apply:  $\geq 2$  mm in men  $\geq 40$  years;  $\geq 2.5$  mm in men  $< 40$  years, or  $\geq 1.5$  mm in women regardless of age. (2) a peak troponin level above 99th percentile and (3) a clinical picture compatible with acute coronary syndrome.

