### **Statistical Analysis**

Baseline characteristics will be summarized using standard descriptive statistics. Comparisons of relevant parameters between groups will be performed by chi-square, Fisher's exact test, Mann-Whitney U, Kruskal-Wallis H test, one-way ANOVA and student t-test, as appropriate. Patients with missing values will be excluded pairwise from analyses. A Cohen's  $\kappa$  test will be used for determination of the intra- and inter-observer agreement for ECG classifications.

Kaplan-Meier analysis will be performed to determine the cumulative long-term mortality rates in different ECG subgroups. The mortality across groups will be compared using log-rank test. A Cox-regression model will be used to perform a survival analysis according to intervention timing and revascularization status. Baseline characteristics with a P value of 0.05 or less in the univariate analysis will be included and a step-down procedure will be applied for selection of final covariates.

**Note:** After data collection, we performed a univariate analysis for mortality and found that many of the baseline parameters, including age, systolic blood pressure, heart rate, baseline

creatinine etc., were significantly associated with long-term mortality. But when these were included in the Cox regression analysis alongside with baseline GRACE risk score, they all lost their statistical significance. Considering GRACE risk score already includes almost all of these variables, we only used GRACE risk score as a covariate in Cox regression model.

The sensitivity, specificity and diagnostic accuracy of STE/non-STE or ACO/non-ACO ECG approaches will be calculated using receiver operating characteristics analysis. As these parameters are highly dependent on the pre-test probability of the disease and pre-test probability of ACO and long-term mortality are closely associated with the presentation type, we will also repeat these analyses after weighing cases for the total number of hospital admissions in the study period.

Statistical analyses will be performed with SPSS (version 24.0; SPSS Inc., Chicago, IL) and MedCalc Software (version 18.2.1 [Evaluation version]; MedCalc Software, Ostend, Belgium).

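### The accuracy result computed first depends on the equal cohort quotas; the admission-weighted analysis that corrects this is planned only as a repeat, is not named primary and has no interval method

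*Combined protocol and SAP*

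**What the plan says.** All references are to the combined protocol and SAP.

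- **Quotas.** Section 2, Patient selection: "We planned to enroll 1000 patients in each of the STEMI, NSTEMI and control groups".
- **Cohort rule and index test.** Section 2 splits STEMI from NSTEMI by sex- and age-specific ST cut-points at the J-point. ECG Interpretation uses the same cut-points for the STE reading. Controls are separated mainly by troponin. One description in section 2 also requires them to be "without any ECG changes during serial follow-up", while the bulleted control definition sets no ECG exclusion.
- **Accuracy analysis.** Statistical Analysis computes sensitivity, specificity and diagnostic accuracy of both ECG approaches by ROC analysis, and then: "we will also repeat these analyses after weighing cases for the total number of hospital admissions in the study period". The reason given is that pre-test probability varies with presentation type.
- **Weights.** Section 2 provides for the counts: "The total admission counts will also be calculated for the weighted analysis of diagnostic accuracy indexes". It lists sensitivity, specificity and both predictive values.
- **Admission mix.** Section 2 gives "around 1000-1500 STEMI patients per year referred for primary PCI" and "This institution also receives STEMI and NSTEMI patients with a 2:1 ratio", and from this concludes: "we expected to enroll 1000 NSTEMI patients before STEMI group is completed".
- **Controls.** "we decided to select these patients from a computer-generated random list". The period that the list covers is not dated.

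The text available for review does not say which accuracy result is primary, and gives no interval or variance method for either.

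**The concern.** When test-positive and test-negative patients are recruited in numbers fixed by design, pooled sensitivity and specificity are no longer properties of the test in the admitted population. They depend on how many patients of each kind were taken. The plan justifies weighting by pre-test probability. For predictive values that is the usual reason. For sensitivity and specificity the dependence arises because the two MI cohorts are sampled on the index test itself.

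The unweighted result therefore describes a 1:1:1 mix that the quotas created. The weighted result describes admissions. With neither named primary, either could be presented as the answer to the study's question. The comparison between approaches is exposed too, because they disagree in both MI cohorts: Type 1b tracings count for the ACO approach only, and Types 1c and 1d for the STE approach only. In addition, if the weights were entered as case counts, the software would treat the weighted total as the number of patients observed, and the intervals would be wrong.

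**Working it through.** The plan states no accuracy figure, so there is none to reproduce. The following is an illustration.

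**Inputs from the document.** 1000 per cohort; a 2:1 ratio of STEMI to NSTEMI; 1000 to 1500 STEMI per year; MI enrolment opened on 1 May 2017, and both MI cohorts were complete by 31 December 2018 (20 months).

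**Assumed inputs.** ACO share p_S = 85% in STEMI (range 70-90%), p_N = 25% in NSTEMI (range 15-40%) and 0% in controls; re-read ECG class equal to cohort label. The 25% is borrowed from the sample-size section, where it may be an ECG-class share rather than an adjudicated one.

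**Step 1: sensitivity of STE.** With cohort weights W_S and W_N, sensitivity = W_S p_S / (W_S p_S + W_N p_N).

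| STEMI:NSTEMI | Calculation | Sensitivity | Change from 1:1, over the ranges |
|---|---|---|---|
| 1:1 (quota) | 850/1100 | 77.3% | - |
| 2:1 | 1700/1950 | 87.2% | +9.9 points (+6.6 to +14.1) |
| 1:2 | 850/1350 | 63.0% | -14.3 points (-10.7 to -17.0) |

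**Step 2: which direction applies.** One year at 1000-1500 STEMI and 2:1 gives 500-750 NSTEMI, short of 1000. Over 20 months the same rates give about 1670-2500 STEMI and 835-1250 NSTEMI, so STEMI would still fill first. NSTEMI finishing first fits only if NSTEMI is the commoner group. The two statements cannot both hold, so both directions are shown.

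**Step 3: relaxing the label assumption.** ECGs are read after all cohorts are complete, and some tracings that meet STEMI criteria are recoded to Type 1b, so class need not equal cohort.
- 10% of ACO cases in the STEMI cohort re-read as not STE: 765/1100 = 69.5% (1:1), 1530/1950 = 78.5% (2:1), 765/1350 = 56.7% (1:2).
- The same, plus 10% of ACO cases in the NSTEMI cohort re-read as STE: 790/1100 = 71.8%, 1555/1950 = 79.7%, 815/1350 = 60.4%.
- ACO in 2% of controls, with controls ten times NSTEMI at 2:1: 850/1120 = 75.9% against 1700/2150 = 79.1%.

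The dependence shrinks in some cases, to 3.2 points in the last, but remains.

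**Step 4: specificity.** With no STE-positive controls, specificity = (W_N(1-p_N) + W_C) / (W_S(1-p_S) + W_N(1-p_N) + W_C). At 1:1:1 this is 1.75/1.90 = 92.1%; at 2:1:5 it is 5.75/6.05 = 95.0%. If 10% of controls were STE-positive, it is 1.65/1.90 = 86.8% and 5.25/6.05 = 86.8%. Specificity may therefore move or not, depending on a share that the document does not fix.

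**Step 5: intervals if weights are treated as case counts.** Let S, N and C be cohort admissions, A = S p_S, B = N p_N, vA = S² p_S(1-p_S)/1000 and vB = N² p_N(1-p_N)/1000. The stratified SE of sensitivity is √(B² vA + A² vB)/(A+B)². The naive SE is √(sens(1-sens)/(A+B)). For specificity with no STE-positive controls, replace A by S(1-p_S) and B by N(1-p_N)+C. The admission totals are assumed.

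| S / N / C | Correct/naive SE, sensitivity | Correct/naive SE, specificity |
|---|---|---|
| 2500 / 1250 / 10000 | 0.0063/0.0068 = 0.93 | 1.43 |
| 1500 / 3000 / 10000 | 0.0131/0.0107 = 1.22 | 1.12 |
| 2000 / 1000 / 10000 | 0.0063/0.0076 = 0.83 | 1.29 |

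Naive intervals can be too wide or too narrow for sensitivity, and are too narrow for specificity in these scenarios.

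**The case against.** The strongest reply is that the plan has already seen the problem. It commits to collecting admission counts and to a weighted analysis, and it ties the weighting to presentation type, which corresponds to the cohorts. That stands: the correction is not missing. What is missing is its priority and its variance method.

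It is also fair to say that pooling is not stated. It is an inference, though weighting to total admissions has little meaning otherwise. The ACO shares and admission totals are assumptions; the dependence itself is algebraic, and only its size rests on them. The absence of an interval method applies to the unweighted analysis as well, but standard output serves there and does not serve for weighted data.

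A reader might infer more than the documents support:
- **That unweighted sensitivity is too low.** This follows only at 2:1; at 1:2 it is too high.
- **That the ranking of the two ECG approaches would reverse.** No detection rates are given, so neither the size nor the sign of any change in their difference can be derived.
- **That weighted specificity intervals would fail badly.** The SE ratio does grow if some controls are STE-positive, but coverage near 50% needs 10,000 control admissions, 10% STE-positive controls and weights run as case counts. The documents establish none of these.
- **That the mortality comparison is compromised.** The comparison that sizes the study lies within NSTEMI and does not depend on the cohort weights.

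**Conclusion.** The point holds as a gap in specification that should be fixed. Followed as written, the plan first produces an accuracy result that depends on the quotas, and does not say that the admission-weighted result takes precedence. On the assumed ACO shares, with class equal to cohort label, STE sensitivity shifts by +6.6 to +14.1 points at 2:1 or by about -11 to -17 points at 1:2. The documents do not settle which applies. The effect on the difference between approaches is real in principle but cannot be quantified. If weights were run as case counts, the correct SE would be about 0.83 to 1.22 times the naive one for sensitivity and 1.12 to 1.43 times for specificity on the assumed totals with no STE-positive controls, and the specificity ratio would be larger with some.

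**What to change.** 1. Name the admission-weighted analysis primary for sensitivity, specificity, predictive values, AUC and the paired difference between the two ECG approaches.
2. Define each weight as the cohort's admissions over its sampling window divided by the patients sampled from it. The MI enrolment dates are given; state the window for the control random list.
3. Take intervals from a bootstrap stratified by cohort, keeping both ECG readings paired within patient.
4. State that the accuracy analysis pools the three cohorts. Show the unweighted data as a table of ECG class by ACO status for each cohort, not as headline pooled accuracy.
5. Reconcile the 2:1 ratio with the expectation that NSTEMI finishes first, and report the observed admission counts.
6. Disclose timing. The Note in Statistical Analysis shows that data had already been collected, so a primary named now is named after that.

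The cost is SAP wording and a little programming, possibly outside the standard ROC output. The admission counts are already due to be collected. Some intervals will widen.
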